### Intervention Arm

The Intervention arm (Tele-HC) will include standard care ***in addition to*** remote physiologic monitoring with a wearable monitor (BodyGuardian®, Preventice) coupled with tailored health coaching. Details of the remote monitoring platform and health-coaching infrastructure are described below.

ECG monitoring, HR, activity, and posture will be collected via on-body sensors while BP and weight data will be collected by off-body sensors linked to BodyGuardian®. Information will be obtained via Bluetooth enabled devices and transmitted to a cloud-based management platform that is alert and protocol driven to assist the care team in patient management. Rhythm monitoring, classification and alerting will be the responsibility of the Mayo Clinic monitoring center in Rochester, MN. Alerts will be communicated to the high touch care team via phone or the secure web-based portal during the hours of 7am-7pm EST, seven days a week. Outside of this time, alerts will be communicated via phone.

The remaining physiological data (HR, activity, posture, BP, and weight) will be uploaded directly to the cloud-based management platform. The cloud-based management platform patient data dashboard will identify, triage, and escalate actionable information for the study team to review via a secure web portal. Patient-generated biometric data will be continuously analyzed and displayed on an hourly basis. Patient-reported symptom information will also be captured. The dashboard uses color-coded (red, yellow, green) to quickly communicate exception data. Live data will be evaluated by the care team 7 days per week from 7am – 7 pm EST with additional monitoring and evaluation of the transmitted data on an as needed basis for calls generated outside of the 12-hour monitoring window.

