An RN will be designated as the primary coach on the high touch study team focused on disease management including symptom recognition, adherence to treatment strategies, care coordination, medication matters, and problem solving. Medication matters include initial medication reconciliation and the organization of resources to obtain medications for patients who have socioeconomic challenges. A RN will also be responsible for managing socio-economic challenges, and providing a nutrition and wellness assessment and goal setting. The high touch study team establishes a patient-centric relationship using techniques of motivational interviewing coupled with a transactional model of communication. Health literacy will be assessed using a validated tool to help personalize coaching interactions. Coaching topics will include the patient's understanding of their disease, establishing goals of health, treatment strategies, medication adherence, and therapy expectations. As the high touch study team identifies knowledge deficits, they customize the education and employ the teach-back

methodology to address the gaps. The high touch study team will engage the patient in collaborative care planning and goal setting to ensure interventions are congruent with the patient's readiness for change, needs, values, culture, desires, and health goals. Patient engagement and self-care management will be measured with the Self-Care of Heart Failure Index in a pre-test/post-test fashion at the time of enrollment and at 60 days post-enrollment.

The research coordinator will screen patients hospitalized with ADHF. Those who meet all inclusion and exclusion criteria will be randomized with unequal allocation, 4:1 Tele-HC intervention to standard care and enrolled in the study. Demographic and clinical data will be collected.

All patients will be assessed at 30 days and 60 days for the occurrence of re-hospitalization and all-cause mortality. De-identified hospital records will be collected so that the study monitor can review to verify cause of re-hospitalization.

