### **7.2.3 Primary Outcomes**

Hypothesis: The 60-day readmission rate will be decreased with the addition of remote monitoring.

To test this hypothesis, a Cochran-Mantel-Haenszel chi-square test of proportions will be used. The stratification factor in this test will be the enrolling clinical site. The primary outcome is all cause readmission, so no adjudication is required for the primary objective. If a participant dies within 60 days of initial hospital discharge prior to any readmission, the participant will be considered as readmitted for the purpose of the primary outcome.

Intention to treat analysis will be used for the primary analysis. If there is loss to follow-up in the groups, the cumulative probability of readmission will be estimated using the Kaplan-Meier method as a sensitivity analysis to the primary analysis. Differences in the hazard rates will be tested using the stratified log-rank test. An additional sensitivity analysis will be conducted using the “per protocol” analysis set (see below), which consists of all subjects that completed the study and were adherent to monitoring.

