### **7.2.4 Secondary and Exploratory Outcomes**

General considerations: The secondary and exploratory endpoints require a variety of standard analytical methods along with sophisticated analytical strategies.

For the secondary endpoint of HF-related readmission, the same analytical approach described for the primary outcome measure will be used. The time to (first) hospital readmission will be modeled using a Kaplan-Meier survival and tested using a stratified log-rank test.

[figure not shown]
For all-cause mortality, the difference in the hazard for death will be tested using a stratified log-rank test on the intention-to-treat sample.

For the exploratory outcomes involving serial measurements originating from the device, longitudinal summary statistics will also be used to condense the longitudinal data stream into meaningful summary measures (e.g., daily mean BP, incremental AUCs) prior to analysis. Longitudinal changes in weight and other continuous measures such as HR and

blood pressures will be modeled using mixed effects models that incorporate random slope and intercept effects.

When the patient is actively monitoring with a BodyGuardian® Control Unit, an activity measure is gathered every 60 seconds. This measure is gathered regardless of the signal quality of the ECG signal or bioimpedance signal quality. When monitoring for 24 hours, a subject should have 1440 samples per day. Adherence for a specific day is measured as the number of activity samples gathered divided by 1440 (expressed as a percentage). Adherence for a given monitoring period will be the number of days where the daily adherence is greater than 80% divided by the total number of days (expressed as a percentage of days monitored).

**Figure 6** Secondary & Exploratory Outcomes Illustration

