### **8.4     *Recording of Clinical Endpoints***

Information on all clinical endpoints will be recorded in the source documentation and in the applicable CRF.

When a hospital readmission occurs, the site coordinator will record the information in the source documentation and in the applicable CRF and will forward all relevant de-identified medical information to the Project Coordinator for review.

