## **10.0 Study Monitoring, Auditing, and Inspecting**

### ***10.1 Study Monitoring Plan***

The investigator will allocate adequate time for monitoring activities. The Investigator will also ensure that the monitor or other compliance or quality assurance reviewer is given access to all study-related documents and study related facilities (e.g. pharmacy, diagnostic laboratory, etc.), and has adequate space to conduct the monitoring visit.

This clinical study will be monitored for appropriate study conduct and data integrity including review of CRFs and parity checks with the source documentation including operator worksheets retained with CRF documentation and hospital charts. Periodic site visits shall be conducted. CRFs will be monitored by the study monitor(s) prior to submission to Mayo Clinic. Monitoring will include comparison of CRFs to source documentation for accuracy and appropriateness, study device accountability, review for/of adverse events, prompt evaluation of unanticipated adverse device effects, and site compliance.

Should discrepancies be identified between the comparison of source documentation and the data contained within the CRF, the most accurate information shall be recorded on a Data Clarification Form (DCF)/or query. Following conclusion of the study, site specific Study Closure Visits will be conducted. Site Study Closure Visits will occur no more than 3 months following study conclusion.

The clinical site will be monitored routinely for fulfillment of Investigator duties and responsibilities, the clinical study as it is conducted in accordance to GCP, EN ISO 14155 and timeliness/completeness of CRF submission to Sponsor. Any evident pattern of non-compliance (i.e. non-reporting of AE or protocol deviations, device accountability inconsistencies, etc.) may initiate remedial actions. If corrective actions are not subsequently undertaken, the clinical site may be withdrawn.

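### HF-related readmission is tested in 7.2.4 but not listed as an endpoint, and nothing in the supplied text keeps the review of readmission cause masked to arm

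*Combined protocol and SAP*

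**What the plan says.** **The test.** Section 7.2.4: "For the secondary endpoint of HF-related readmission, the same analytical approach described for the primary outcome measure will be used". The primary method is a Cochran-Mantel-Haenszel test stratified by site. Section 7.2.2 leaves secondary outcomes unadjusted for multiplicity.

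**The endpoint lists.** Sections 3.2 and 4.6.2 list time to readmission or death, number of readmissions or ER visits, and all-cause mortality. HF-related readmission is in neither list, nor among the exploratory outcomes in 4.6.3.

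**Who looks at cause.** Section 4.3 (Intervention Arm): "De-identified hospital records will be collected so that the study monitor can review to verify cause of re-hospitalization". In section 8.4 the site coordinator records the readmission and "will forward all relevant de-identified medical information to the Project Coordinator for review".

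**What else monitoring covers.** Section 10.1: "CRFs will be monitored by the study monitor(s) prior to submission to Mayo Clinic", and further: "Monitoring will include comparison of CRFs to source documentation for accuracy and appropriateness, study device accountability, review for/of adverse events".

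**Where the device is used.** Section 4.3 describes the Tele-HC arm as standard care plus "remote physiologic monitoring with a wearable monitor (BodyGuardian®, Preventice) coupled with tailored health coaching".

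**Adjudication.** Section 7.2.3: "The primary outcome is all cause readmission, so no adjudication is required for the primary objective". Nothing comparable is said for HF-related readmission.

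**The concern.** Whether a patient was readmitted is close to a matter of fact. Whether the readmission was HF-related is a judgement, because heart failure can be one of several reasons for an admission. The reason that section 7.2.3 gives for needing no adjudication, that the primary counts every cause, does not carry over to a cause-specific endpoint.

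A worn sensor with coaching cannot be hidden from patients or staff, and no masking is described. If whoever settles the cause can know the arm, borderline admissions may be sorted differently in the two arms. The resulting difference would look like a treatment effect, or would hide one, on the endpoint closest to the intervention's stated purpose of earlier detection of decompensation (section 2.4.5).

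**Working it through.** **1. Which endpoints depend on cause.**
- Primary (4.6.1, 7.2.3), all-cause readmission or death: no.
- Time to readmission or death (4.6.2): no.
- Number of readmissions or ER visits (4.6.2): no.
- All-cause mortality (4.6.2): no.
- HF-related readmission (7.2.4 only): yes.

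The exposure is confined to one endpoint, which the plan's own lists omit.

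**2. Who settles cause.** Section 4.3 names the study monitor and section 8.4 the Project Coordinator. Neither gives a criterion for HF-related, and the two sections do not refer to each other.

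**3. Whether the arm can be known.** Section 10.1 puts CRF review, comparison with source and device accountability within monitoring. Only Tele-HC patients have the device, and the adverse event CRF in section 8.5 carries the device kit and serial number. A person doing this work can therefore learn the arm. De-identification removes identity. No section says that it also removes mention of the arm, BodyGuardian, alerts or coaching. The Project Coordinator's access to allocation is not described.

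**4. Sensitivity of the test (illustration).** The plan states no figure for HF-related readmission. Its one sample-size figure, for the all-cause primary (section 7.1), reproduces. With rates 0.25 and 0.125 and mean 0.1875:

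n = [1.960 × √(2 × 0.1875 × 0.8125) + 0.842 × √(0.1875 + 0.1094)]² / 0.125² ≈ 152 per group.

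Inputs for the illustration:
- N = 304 (section 7.1), split 4:1 (section 4.2): 304/5 ≈ 61 standard care and 243 Tele-HC.
- True HF-readmission rate p, equal in both arms: **assumed**, 8% to 25%, central value 12.5%.
- Fraction m of Tele-HC HF readmissions relabelled as non-HF: **assumed**, 0 to 30%.
- Uncorrected two-sided chi-square at 0.05, one stratum, exact binomial enumeration.

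Observed Tele-HC rate = p(1 − m), so the risk ratio is 1 − m. At p = 12.5%, m = 10% gives 11.25% and m = 30% gives 8.75%, that is, ratios of 0.90 and 0.70. In counts, 243 × 0.125 ≈ 30 patients, so three to nine relabelled.

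Chance of a nominally significant result favouring Tele-HC with no true effect:

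| m | p = 12.5% | p from 8% to 25% |
|---|---|---|
| 0 | 3.0% | 2.8% to 3.2% |
| 10% | 5.6% | 5.3% to 6.8% |
| 20% | 9.8% | 8.5% to 14.6% |
| 30% | 16.4% | 13.3% to 27.6% |

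The error could run the other way. A reviewer who sees weight or rhythm alerts might call more Tele-HC admissions HF-related. With 10% to 30% more so labelled, 12.5% × 1.10 = 13.75% and 12.5% × 1.30 = 16.25%, ratios of 1.10 to 1.30 against the intervention.

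**The case against.** The strongest reply is that this is ordinary source verification. Section 4.3 has the monitor verify cause, section 8.4 has the site coordinator record the readmission, and section 10.1 compares CRFs with source. No section gives the monitor authority to reclassify an admission. This stands in part: a reader might infer that the monitor decides the cause, but the documents do not say so. They also do not say who does, or by what criterion.

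Secondly, knowledge of the arm is a possibility, not a stated fact. Section 10.1 speaks of one or more monitors, so different people could verify cause and account for devices. A reader might infer that one person does both. Nothing requires that, and nothing prevents it.

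Thirdly, a reader might infer that the plan will produce a false HF-specific benefit with a risk ratio of 0.90 to 0.70. The documents do not support this. Those ratios only restate the assumed relabelling, in one assumed direction, and the 12.5% HF rate has no source: section 7.1 uses 12.5% as the all-cause rate under treatment.

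Fourthly, the endpoint may be a leftover, since only section 7.2.4 names it. If the test is deleted, the bias point disappears. This stands, and it is why the first step below concerns the endpoint's status.

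Lastly, masking or cause coding may be set out in the case report forms (Appendix 15.3), the Data and Safety Monitoring Plan (Appendix 15.4) or section 8.8, whose contents are not in the text reviewed. That cannot be excluded. The mismatches between 7.2.4 and the endpoint lists, and between 4.3 and 8.4, would still need reconciling.

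**Conclusion.** The point holds in a limited form. The plan commits to testing one cause-dependent endpoint that it does not list. It names two different roles for reviewing readmissions, gives no criterion for HF-related, and in the supplied text does not keep the arm from whoever reviews cause.

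This is a gap in protection. Bias has not been shown, and its direction and size are unknown. The percentages above rest wholly on assumed rates and one-sided relabelling. They show only that a handful of arm-dependent decisions, about three to nine patients at an assumed 12.5%, would matter to this test. The all-cause primary, the listed secondary endpoints and mortality do not depend on the classification. The change is worth making because it is cheap.

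**What to change.** 1. **Settle the endpoint's status.** Either add HF-related readmission to 3.2 and 4.6.2, or delete its test from 7.2.4. If it is deleted, steps 2 and 3 fall away.
2. **If it is kept, mask the review.** When de-identifying readmission records, the site coordinator also removes references to arm, BodyGuardian, alerts and coaching. Cause is then classified from those records by one existing role, named identically in 4.3 and 8.4, that does not do device accountability. State whether that role has access to allocation.
3. **Fix the criterion before any outcome is reviewed.** Say what counts as HF-related, including whether a secondary HF diagnosis qualifies. Use the readmitting hospital's principal discharge diagnosis as a sensitivity analysis. It should not be imposed as the only definition: the index admission may qualify on a secondary ADHF diagnosis (5.1), and treating clinicians can know the arm too.

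**Cost.** Wording in 3.2, 4.3, 4.6.2, 7.2.4 and 8.4, and one more redaction step on records already being de-identified. No new assessor is intended, provided an existing role without device accountability can take the review. Masking may be imperfect, since a record can reveal the arm indirectly. The primary analysis does not change.

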#### **4.4 *Intervention Protocol (Tele-HC)***

Intake – high touch study liaison (pre hospital discharge)

- Program introduction
- Review medical history
- Introduce team members

On boarding- study team members or staff contracted by clinical site

- Patient visit prior to hospital discharge, medication reconciliation, sodium intake reconciliation, BodyGuardian® application

Stabilization phase – high touch study team member (day 1-14 post discharge)

- Baseline physiological data
- Daily review of patient generated data
- Medication adherence
- Low sodium adherence
- Reinforce self-care behaviors
- Daily touches at a minimum

Optimization phase – high touch study team member (day 15-60 post discharge)

[figure not shown]
- Daily review of patient generated data
- Reinforce self-care behaviors
- Screen for depression and sleep apnea
- Optimize disease management (in collaboration with primary cardiologist)
- Targeted touches

Measured variables (to be obtained from both groups)

- 6 minute walk test (pre-discharge, 60 day)
- ECG (onboarding)
- SCHFI Self-care index and MLHFQ Heart Failure questionnaire (onboarding, 60 day)
- NYHA functional class (pre-discharge, 60 day)
- 60 day readmission
- Unscheduled clinic, hospital and/or ER visits
- Echocardiogram derived EF within 6 months prior to randomization
- Pre-discharge metabolic profile, creatinine, Hb, K, Na, GFR

Data collection obtained from clinically indicated investigations include the 6 minute walk, ECG, EF, chest x-ray, and blood test.

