#### **4.6.3 Exploratory Outcomes**

- Change in self-care score at baseline and at end of study in both groups
- NYHA functional class at baseline and at end of study in both groups
- 6 minute walk results at baseline and at end of study in both groups
- Quality of life scores (Minnesota Living with HF) at baseline and at end of study in both groups
- Correlation of data obtained from the BodyGuardian® remote monitoring platform with clinical outcomes

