#### **4.7.2 Self-Care and Life Quality Evaluation**

Each subject will be asked to complete two separate questionnaires at baseline prior to use of the remote monitoring system and again at completion of the study. The first questionnaire is the Self-Care of Heart Failure Index (SCHFI), and the second is the Minnesota Living with Heart Failure Questionnaire (MLHFQ), which are validated tools for quantifying self-care and quality of life.

The SCHFI is comprised of three subscales: self-care maintenance (choice of behaviors used to maintain physiologic stability), self-care management (response to symptoms when they occur) and self-care confidence. The maintenance, management, and confidence subscales are comprised of 5, 6, and 4 Likert questions, respectively. A higher score on the SCHFI indicates improved self-care.

The MLHFQ consists of 21 questions that use a 6-point Likert scale. The physical dimension score for the MLHFQ is the summation of 8 questions (e.g., Did your heart failure make you sit or lie down to rest during the day?), while the emotional dimension score is the summation of 5 other questions (e.g., Did your heart failure make you worry?). A lower score on the MLHFQ indicates higher quality of life.

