## 6.0 Study Procedures

### 6.1 Study Schedule

Data Collection	Screening through 2 working days post hospital dismissal	Follow-up Visits	
		30 Days (-2/+7 days)	60 Days (+/- 14 days)
Informed Consent/Assessment of Eligibility	X		
Randomization	X		
Demographics/Medical History	X		
Medications	X	X	X
ECG (within 2 weeks)	X		
6 minute walk (to be taken from medical record if done)	X		X
Blood work (Creatinine, Hb, potassium, sodium, GFR)	X		
Ejection fraction (within 6 months)	X		
Home visit (BodyGuardian® implementation, medicine	X 		

reconciliation, nutrition review) 			
Self-Care of Heart Failure Index (SCHFI) 	X 		X 
Minnesota Living with Heart Failure Questionnaire (MLHFQ)	X 		X 
New York Heart Class	X		X
Health Literacy Measure	X		
Medical Outcomes General Adherence Measure (PHQ9)	X		
Subject training	X		
Follow-up outcomes/study endpoint events		X	X

*Intervention Arm only*

*The purpose of these measures is to summarize participant characteristics that may relate to later adherence behaviors (e.g., wearing the monitor and measuring body weight as instructed). The participant data will also be used to provide further context to qualitative interview data.*

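### The SCHFI and MLHFQ baselines are dated inconsistently and never required before randomization, so these exploratory self-report scores may be influenced by arm

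*Combined protocol and SAP*

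**What the plan says.** Four places in the combined protocol and SAP date the baseline of the Self-Care of Heart Failure Index (SCHFI) and the Minnesota Living with Heart Failure Questionnaire (MLHFQ).

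- Section 4.3, Intervention Arm (SCHFI only): "at the time of enrollment and at 60 days post-enrollment". The same section describes eligible patients as being randomized and enrolled in one step.
- Section 4.4: "SCHFI Self-care index and MLHFQ Heart Failure questionnaire (onboarding, 60 day", in a list introduced as "Measured variables (to be obtained from both groups".
- Section 4.7.2 (both forms): "at baseline prior to use of the remote monitoring system".
- Section 6.1: both forms sit in the column "Screening through 2 working days post hospital dismissal". That column also holds consent, randomization, subject training and the home visit for the intervention arm only.

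Section 4.4 describes onboarding as "Patient visit prior to hospital discharge, medication reconciliation, sodium intake reconciliation, BodyGuardian® application". It is listed after "Intake – high touch study liaison (pre hospital discharge", where the program and the team are introduced. Daily coaching contact starts on day 1 after discharge.

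Section 4.6.3 makes both instruments exploratory. For the SCHFI it lists "Change in self-care score at baseline and at end of study in both groups". For the MLHFQ it lists scores at the two time points in both groups, without naming change.

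**The concern.** A baseline protects a randomized comparison only if allocation cannot affect it. Here the patient cannot be blinded to a wearable monitor and a coach, and both instruments are self-reported. The SCHFI also measures self-care maintenance, management and confidence, which are what the coaching aims to change. If the form is completed after the patient knows the arm, or after the team has begun work, the score may already carry part of the intervention's effect or a reaction to the assignment.

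Any such shift would enter the between-arm difference in change directly. It would also weaken the score as an adjustment variable. The footnote in Section 6.1 gives a further use, relating these measures to later adherence, and a score taken after allocation is less suited to that as well.

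**Working it through.** **1. The plan's own figures.** There is no design calculation, SD or expected change for the SCHFI or MLHFQ comparison. The only design calculation is for readmission, in Section 7.1: 25% against 12.5%, two-sided alpha 0.05, 80% power. With mean proportion 0.1875:

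n = (1.960 × √(2 × 0.1875 × 0.8125) + 0.842 × √(0.25 × 0.75 + 0.125 × 0.875))² / 0.125² ≈ 152 per group.

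This matches the stated 152. The timing of the questionnaires does not affect it.

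**2. The four timings side by side.**

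| Place | Baseline timing | Requires completion before randomization? | Excludes earlier Tele-HC contact? |
|---|---|---|---|
| 4.3 Intervention Arm (SCHFI) | Enrollment | No; patients are randomized and enrolled together | Not stated |
| 4.4 | Onboarding | No; intake and onboarding are Tele-HC steps, so in that arm they follow allocation | No; intake comes first, and the visit includes reconciliation |
| 4.7.2 | Before device use | No | Excludes device use only |
| 6.1 | Any time to 2 working days after dismissal | No; randomization is in the same column | No; the window overlaps coaching from day 1 |

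A site could follow Sections 4.4 and 4.7.2 exactly and still collect the form after the patient knows the arm, has met the team, and has gone through medication and sodium reconciliation, provided the device is not yet on.

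**3. What a shift would do.** Scale both scores to SD 1. Let r be the pre/post correlation, d the true day-60 effect, and b a baseline shift in the Tele-HC arm only, positive when it looks like better self-care.

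- Difference in change = d − b.
- Day-60 difference adjusted for the shifted baseline = d − r × b, because the regression slope is r.
- Day-60 difference that ignores baseline = d.

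**4. Illustration.** None of these values of b, r or d is in the documents. They are assumptions: b from 0.1 to 0.3, r from 0.3 to 0.7, and d of 0 or 0.4. Arm sizes follow Section 4.2 (4:1 of 304): 304 × 4/5 ≈ 243 and 304 × 1/5 ≈ 61. Scores are normal, with 4,000 simulated trials per setting and two-sided 5% tests. Three of the nine combinations of r and b, including both extremes:

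| r | b | Change, d = 0: estimate (rejects) | Adjusted, d = 0: estimate (rejects) | Change, d = 0.4 | Adjusted, d = 0.4 |
|---|---|---|---|---|---|
| 0.3 | 0.1 | −0.096 (9%) | −0.028 (5%) | 0.300 | 0.369 |
| 0.5 | 0.2 | −0.202 (30%) | −0.103 (13%) | 0.203 | 0.303 |
| 0.7 | 0.3 | −0.303 (78%) | −0.212 (54%) | 0.098 | 0.189 |

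The estimates agree with d − b and d − r × b. Adjusting for a shifted baseline reduces the bias but does not remove it. A positive b hides benefit. A negative b would exaggerate benefit by the same amount.

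**The case against.** The strongest reply is that the timings are compatible. Enrollment, onboarding and before device use can all be met at one pre-discharge contact, with the forms completed before the monitor goes on. Section 4.3 calls the SCHFI a pre-test/post-test measure, which shows that a pre-intervention score was intended. The Section 6.1 column is an outer window for every screening item, and Section 4.7.2 narrows it for patients who get the device. The content of the schema (Section 4.5) and of the case report forms (Appendix 15.3) is not in the available text, and either might fix the order.

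Much of this stands, and it rules out several stronger readings that a reader might infer.

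- *That the baseline is contaminated by arm.* The text permits this but does not show it. No size or direction can be derived.
- *That controls are measured in a different setting.* No onboarding contact is described for standard care, but Section 4.4 asks for the measures in both groups and uses the same label for the ECG. Onboarding may simply name the baseline time point. The control timing is loosely defined; a difference between arms is not demonstrated.
- *That every change score is biased.* Section 4.6.3 names change for self-care only, and Section 7.2.4 gives no between-arm method specific to either instrument.
- *That the PHQ-9 has the same fault.* It is collected at baseline only and is not an outcome. No fault is shown.

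The reply does not supply a requirement that the forms precede randomization. Section 4.7.2 excludes device use, but not knowledge of the arm, the intake contact or reconciliation. For controls, who receive no device, it sets no limit.

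**Conclusion.** The point holds as a minor one. The baseline timings are inconsistent, and none of the available text requires the SCHFI and MLHFQ before randomization, so the Tele-HC baseline may be completed after allocation is known and after early intervention contact. This rests on reading intake and onboarding as post-allocation steps in that arm, and on patients being unblinded, as the nature of the intervention implies.

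The reach is limited to exploratory outcomes. Readmission or death, time to event, visit counts and mortality do not use these scores. The size is unknown: b for a change comparison and r × b for an adjusted one, with b and r not given in the documents and the sign of b open. The simulated range shows sensitivity to assumed values and does not estimate what will happen in this trial.

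**What to change.** In Section 4.3 (Intervention Arm), Section 4.4, Section 4.7.2 and the Section 6.1 schedule, state that the SCHFI and MLHFQ are completed after consent and before randomization in both arms. Record the date and time of each form and of randomization.

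In Section 7.2.4, specify a between-arm comparison of 60-day scores adjusted for the pre-randomization score and the Section 4.2 stratification factors: site, sex and NYHA class. Where any form was completed after randomization, add a sensitivity analysis that compares day-60 scores without using that baseline. It avoids the shift at some cost in precision: in the model above the adjusted residual variance is 1 − r², so at r = 0.5 adjustment would have left 0.75 of the unadjusted variance.

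The cost is the order of the forms and a note in the schedule. NYHA class must already be known before randomization because it is a stratification factor, so a pre-randomization assessment exists to which the forms can be attached. The downside is that assignment may be slightly delayed in some patients. The change does not address open-label reporting at day 60, which is a separate limitation.
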